2. LIST OF ABBREVIATIONS

See Medicine Glossary:
<http://glossary>

Term	Definition / description
AE	Adverse Events
AESI	Adverse Event of Special Interest
ALT	Alanine Aminotransferase
AST	Aspartate Aminotransferase
AUC _{0-tz}	Area under the concentration-time curve of the analyte in serum over the time interval from 0 to the last quantifiable drug concentration
AUC _{0-∞}	Area under the concentration-time curve of the analyte in serum over the time interval from 0 extrapolated to infinity
BCVA	Best Corrected Visual Acuity
BI	Boehringer Ingelheim
BLRM	Bayesian Logistic Regression Model
BMI	Body mass index
CI	Confidence Interval
C _{max}	Maximum measured concentration of the analyte in serum
CTP	Clinical Trial Protocol
CTR	Clinical Trial Report
CV	Arithmetic Coefficient of Variation
CVC	Combined Vascular Complex
DBLM	Database Lock Meeting

Term	Definition / description
DILI	Drug induced liver injury
DLE	Dose Limiting Event
DVC	Deep Vascular Complex
ECG	Electrocardiogram
EOS	End of Study
ES	Enrolled set
FAZ	Foveal Avascular Zone
FTR	Full Thickness Retina
gCV	Geometric Coefficient of Variation
█	█
gMean	Geometric Mean
HR	Heart Rate
█	█
IPD	Important Protocol Deviation
IVT	intravitreal
█	█
LLT	Lower Level Term
IQRMP	Integrated Quality and Risk Management Plan
Max	Maximum
MedDRA	Medical Dictionary for Drug Regulatory Activities
MD	Multiple Dose
Min	Minimum
N	Number non-missing observations
OCT	Optical Coherence Tomography
OCTA	Optical Coherence Tomography Angiography
P10	10 th percentile
P90	90 th percentile
PK	Pharmacokinetic
PKS	PK parameter analysis set
Q1	1 st quartile
Q3	3 rd quartile
QRS	Combination of the Q, R, and S waves in electrocardiogram

Term	Definition / description
QT	Time between start of the Q-wave and the end of the T-wave in an electrocardiogram
QTcB	QT interval corrected for heart rate using the method of Bazett
QTcF	QT interval corrected for heart rate using the method of Fridericia
RAGe	Report Appendix Generator system
REP	Residual Effect Period
SD	Standard Deviation
SRD	Single Rising Dose
SVC	Superficial Vascular Complex
t _{max}	Time from dosing to maximum measured concentration of the analyte in serum
TS	Treated Set
TSAP	Trial Statistical Analysis Plan
ULN	Upper Limit of Normal
█	█
VEGF	Vascular Endothelial Growth Factor
WHO-DD	World Health Organization Drug Dictionary

3. INTRODUCTION

As per ICH E9 (1), the purpose of this document is to provide a more technical and detailed elaboration of the principal features of the analysis described in the protocol, and to include detailed procedures for executing the statistical analysis of the primary and secondary variables and other data.

This TSAP assumes familiarity with the Clinical Trial Protocol (CTP), including Protocol Amendments. In particular, the TSAP is based on the planned analysis specification as written in CTP Section 7 “Statistical Methods and Determination of Sample Size”. Therefore, TSAP readers may consult the CTP for more background information on the study, e.g., on study objectives, study design and population, treatments, definition of measurements and variables, planning of sample size, randomization.

Study data (including data entered in the RAVE EDC system and external data provided by suppliers) will be stored in a Clinical Data Repository (CDR).

Pharmacokinetic (PK) parameters will be calculated using Phoenix WinNonlin™ software (version 8.1 or higher, [REDACTED]) or SAS Version 9.4 (or later version).

The statistical analyses will be performed within the validated working environment CARE, including SAS™ (current Version 9.4, by [REDACTED]), and a number of SAS™-based tools (e.g., macros for the analyses of AE data or laboratory data; Report Appendix Generator system (RAGe) for compilation/formatting of the CTR appendices).

4. CHANGES IN THE PLANNED ANALYSIS OF THE STUDY

All analyses as planned in the CTP will be performed and are described in more detail in this TSAP.

For a more accurate reflection of the data, the term 'combined vascular complex' (CVC) for FAZ-related parameters has been renamed as 'full thickness retina' (FTR). For the MD part, the main assessment for FAZ parameters in FTR was changed to a manual grading of the 3mm OCTA scans i.e., the MD part endpoints related to FAZ area in FTR mentioned in the CTP are considered to be based on manually graded data for 3mm scan size. If an OCTA measurement is done for a specific scan size, this will be indicated in the endpoint label. For other OCTA endpoints where a measurement was not performed for a specific scan size, it will be deemed that the measurement was made primarily based on a 6mm scan size and if this was not possible then otherwise taken from a 3mm scan size.

Sensitivity statistical analysis of the efficacy endpoints using LOCF will not be performed as the handling of missing data is taken into account within the MMRM approach

5. ENDPOINTS(S)

The pharmacokinetic and pharmacodynamic parameters listed in Section 2.2 of the CTP for drug BI 764524 will be calculated according to relevant BI internal procedure.

5.1 PRIMARY ENDPOINT(S)

Section 2.1.2 of the CTP:

SRD part:

- Number of patients with dose limiting events (DLEs) from drug administration till day 8 (7 days after treatment).

For definition of DLEs, refer to [Section 7.4](#).

MD part:

- number of patients with drug related adverse events (AEs) from drug administration till end of study (EOS)

5.2 SECONDARY ENDPOINT(S)

5.2.1 Key secondary endpoint(s)

This section is not applicable as no key secondary endpoints have been defined in the CTP.

5.2.2 Secondary endpoint(s)

Section 2.1.3 of the CTP:

SRD part:

- number of patients with drug related AEs at EOS
- number of patients with ocular AEs (eye disorders) at EOS

MD part:

- change from baseline of the size of the FAZ area in optical coherence tomography angiography (OCTA) in superficial vascular complex and full thickness retina at Visit 5.
- change from baseline of the size of the FAZ area in optical coherence tomography angiography (OCTA) in superficial vascular complex and full thickness retina at Visit 7.
- change from baseline of BCVA at Visit 3
- change from baseline of BCVA at Visit 4
- change from baseline of BCVA at Visit 5
- change from baseline of BCVA at Visit 6
- change from baseline of BCVA at Visit 7
- change from baseline of Central retinal thickness (SD-OCT) at Visit 3
- change from baseline of Central retinal thickness (SD-OCT) at Visit 4
- change from baseline of Central retinal thickness (SD-OCT) at Visit 5
- change from baseline of Central retinal thickness (SD-OCT) at Visit 6
- change from baseline of Central retinal thickness (SD-OCT) at Visit 7
- number of patients with ocular AEs (eye disorders) at EOS

Note that the above FAZ area in FTR is understood to be the FAZ area in FTR for the 3mm scan size, manually graded.

5.3 FURTHER ENDPOINT(S)

Concise summary of efficacy endpoints to be described in CTR:

SRD Part

FAZ area in superficial vascular complex

FAZ area in full thickness retina

BCVA

Central Retinal Thickness

6. GENERAL ANALYSIS DEFINITIONS

6.1 TREATMENT(S)

For basic study information on treatments to be administered, assignment of treatment groups, selection of doses, refer to CTP Sections 3 and 4.

The trial will consist of an SRD part followed by an MD part. The SRD part will be conducted open-label, non-randomized, and uncontrolled, whereas the MD part will be single-masked, randomized and sham-controlled.

It was planned to assign up to 45 patients in total, up to 15 in the SRD part in (3 sequential dose groups comprising at least 3 patients each) and 30 in the MD part (20 patients on BI 764524 and 10 patients on sham injection).

With recruitment completed, the actual numbers enrolled are 12 patients in the SRD part and 32 in the MRD part (3 patients discontinued and were replaced).

For details of dosage and formulation see [Tables 6.1:1](#) and [6.1:2](#) below.

Table 6.1: 1 Treatments and labels used in the analysis – SRD part

Dose group	Treatment	Description	Short label
1	D	BI 764524 █████ SRD	BI █████ SRD
2	E	BI 764524 █████ SRD	BI █████ SRD
3	F	BI 764524 █████ SRD	BI █████ SRD

Table 6.1: 2 Treatments and labels used in the analysis – MD part

Dose group	Treatment	Descriptive	Short label
1	A	BI 764524 █████g	BI █████ MD
2	S	Sham injection	Sham MD

Section 7.3.4 of the CTP:

For BI 764524 the residual effect period (REP) after IVT administration is not known. Therefore, all AEs with an onset between start of treatment and the respective EOS visit will be assigned to the on-treatment period for evaluation.

The following separate study phases will be defined for the analyses of AEs:

- **Screening** (ranging from 0:00h (midnight) on the day of informed consent until the first administration time of BI 764524)
- **On treatment**
 - **BI treatment** (separately for each treatment, ranging from the time of first administration of BI 764524 until 0:00h (midnight) on the day after trial completion date)

The following AE displays will be provided in the report:

Section 15.3 (presented separately for SRD and MD part) and Appendix 16.1.13.1.8 (for ClinicalTrials.gov and EudraCT) of the CTR displays:

In these displays, the -on- treatment phase will be analysed (labelled with the short label of the study treatment). Screening will not be included in this analysis.

The following totals will be provided in section 16.1.13.1.8 in addition:

- a total over all on-treatment phases ("Total")
- a total over all on-treatment phases in the SRD part ("Total - SRD part")
- a total over all on-treatment phases in the MD part ("Total - MD part")
- a total over all on-treatment phases involving BI 764524 ("BI Total")

- a total over all on-treatment phases involving BI 764524 in the SRD part ("BI Total – SRD part")
- a total over all on-treatment phases involving BI 764524 in the MD part ("BI Total – MD part")

In Section 15.4 and Appendix 16.2 (Listings) of the CTR displays, the screening period will be included and no totals will be provided.

Tables of vital signs and laboratory values will present results for the above mentioned on treatment phase.

For detailed information on the handling of the treatments refer to the Technical TSAP ADS (analysis data set) plan and the Analysis Data Reviewers guide.

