## 7. STATISTICAL METHODS AND DETERMINATION OF SAMPLE SIZE

### 7.1 STATISTICAL DESIGN – MODEL

This trial will consist of an SRD part followed by an MD part. The SRD part will be conducted non-randomized, open-label, and uncontrolled. MD part will be conducted single-blind, randomized and sham-controlled. The main objectives of this trial will be assessed by calculating descriptive statistics on DLEs and drug related AEs. For the MD part these will be compared descriptively between the treatment groups.

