#### 7.3.4 Safety analyses

Safety will be assessed as defined by the endpoints listed in Section [2.1.2](#) and [2.2.2](#) based on the treated set (TS). Safety analyses will be descriptive in nature and will be based on BI standards.

For all analyses the treatment actually administered (= treatment at onset) to the patient will be used (any deviations from the randomized treatment will be discussed in the minutes of the Report Planning Meeting).

Treatments will be compared in a descriptive way. The sham group in the safety evaluation will consist of all patients treated with sham injection, regardless of the dose group in which they were treated. The test treatment groups will be compared to the sham group in a descriptive way. Tabulations of frequencies/proportions will be used for the evaluation of categorical (qualitative) data, and tabulations of descriptive statistics will be used to analyse continuous (quantitative) data.

Measurements (such as ECGs, vital signs, or laboratory parameters) or AEs will be assigned to treatments (see Section 4.1) based on the actual treatment at the planned time of the measurement or on the recorded time of AE onset (concept of treatment-emergent AEs). Therefore, measurements planned, or AEs recorded prior to first intake of trial medication will be assigned to the screening period. For BI 764524 the residual effect period (REP) after IVT administration is not known. Therefore, all AEs with an onset between start of treatment and the respective EOS visit will be assigned to the on-treatment period for evaluation. These assignments including the corresponding time intervals will be defined in detail in the TSAP. Note that AEs occurring after the last per protocol contact but entered before database lock will be reported to Pharmacovigilance only and will not be captured in the trial database.

Additionally, further treatment intervals (called analysing treatments) may be defined in the TSAP in order to provide summary statistics for other than above periods, such as combined treatments, on-treatment totals, or periods without treatment effects (such as screening and post-study intervals).

Adverse events will be coded using the Medical Dictionary for Regulatory Activities (MedDRA). Frequency, severity, and causal relationship of AEs will be tabulated by treatment, system organ class and preferred term. SAEs, AESIs (see Section 5.2.7.1) and other significant AEs (according to ICH E3) will be listed separately.

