6.7 BASELINE, TIME WINDOWS AND CALCULATED VISITS

The baseline value is defined as the last measurement before first administration of trial medication (= value at V2, in case no actual time is given in data).

Section 5.1 of the CTP:

For the endpoints, baseline is defined as the value at Visit 2; if not measured at Visit 2 then baseline is the value at Visit 1.

This rule will also apply to the additional endpoint, [REDACTED].

Section 6.1 of the CTP:

For visit schedule, refer to Flow Chart I and Flow Chart II. The acceptable time windows for visits are given in the Flow Charts. For planned individual serum concentration sampling times, refer to appendix 10.1.

SRD Part:

Adherence to time windows will be checked via the consistency check listings at the RPM/DBLM.

MD Part:

Analysis of AE data, potentially clinically significant abnormal laboratory values, concomitant medication or non-drug therapies, as well as use of rescue therapy will not be based on visits. Therefore, no assignment to time windows will be necessary for such data.

All other safety and efficacy measurements will be assigned to visits based on extended time windows around the planned visit dates, defined relative to the day of first trial treatment (which is scheduled for Visit 2). These extended time windows are defined in [Table 6.7: 1](#), [Table 6.7: 2](#), and [Table 6.7: 3](#).

Only one observation per time window will be selected for statistical analysis at a particular visit – the value which is closest to the protocol planned visit day will be selected, except for safety lab where the worst scenario is chosen. If there are two observations which have the same difference in days to the planned day, the later value will be selected.

For [REDACTED], the worst case scenario will be used (i.e. highest value will be taken) if more than one measurement is made in the same time window.

Section 5.2.5.1 of the CTP:

Central ECG lab evaluation will be performed for all ECGs indicated in the Flow Chart I and Flow Chart II. For all ECGs this will include the intervals RR, PR, QRS and QT measured semi-automatically. The screening ECGs will be checked for abnormalities.

The baseline value of an ECG variable is defined as the mean of the ECG measurements prior to drug administration.

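### Read as written, SAP 6.1 gives sham patients no on-treatment phase, and the Treated Set (protocol 7.3, SAP 6.3) excludes the non-randomised SRD patients

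*SAP*

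**What the plan says.** **On-treatment phase.** SAP 6.1 defines the phases used to analyse adverse events (AEs). Screening runs from the day of consent "until the first administration time of BI 764524". Under the on-treatment heading there is one entry, for BI treatment, defined as "separately for each treatment, ranging from the time of first administration of BI 764524 until 0:00h (midnight) on the day after trial completion date". Table 6.1: 2 lists sham as a treatment with its own label, but no phase is written for it. The AE displays for CTR Section 15.3 and for trial disclosure use the on-treatment phase and leave Screening out. SAP 6.1 also ties the vital-sign and laboratory tables to this phase, and SAP 7.8.2 restricts the eDISH plot to the on-treatment period.

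**Treated Set.** Protocol 7.3 and SAP 6.3 use the same definition: a patient must have been randomised and must have received one or more doses, active or sham. Protocol 7.6 says that the SRD part has no randomisation. The primary endpoints of both parts (protocol 7.3.1), all safety analyses (SAP 7.8) and the baseline summaries (SAP 7.1) are based on the Treated Set. Protocol 7.3 also builds the pharmacokinetic set from it.

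**The concern.** The primary endpoint of the multiple-dosing (MD) part is the number of patients with drug-related AEs, and the value of the sham arm for safety is the contrast with it. Protocol 7.1 says of the summaries of dose-limiting events and drug-related AEs: "For the MD part these will be compared descriptively between the treatment groups". Protocol 7.3.4 adds: "The test treatment groups will be compared to the sham group in a descriptive way". That section leaves the exact time intervals to the SAP, and SAP 6.1 is where they are set out. If the start event cannot occur in one arm, the written rule gives that arm no column in the comparison.

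The Treated Set has the same kind of fault in the other part. Its definition sets a condition that no SRD patient can meet, although the SRD primary endpoint is to be tabulated on that set.

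In both cases a programmer has to depart from a stated definition to produce the intended tables, and nothing in SAP Section 4 authorises the departure.

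**Working it through.** The plan states no figure to reproduce. The check sets the definitions side by side and counts whom each one leaves out.

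**(a) Which event starts treatment?**

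| Place | Event | Can it occur for sham? |
|---|---|---|
| SAP 6.1, end of Screening | "until the first administration time of BI 764524" | No |
| SAP 6.1, on-treatment phase | "separately for each treatment, ranging from the time of first administration of BI 764524 until 0:00h (midnight) on the day after trial completion date" | No |
| SAP 6.1, rule taken from protocol 7.3.4 and repeated in SAP 7.8.1 | "all AEs with an onset between start of treatment and the respective EOS visit will be assigned to the on-treatment period for evaluation" | Yes |
| Protocol 7.3.4, screening | "AEs recorded prior to first intake of trial medication will be assigned to the screening period" | Yes, if sham counts as trial medication |
| SAP 6.7, visit windows | "defined relative to the day of first trial treatment" | Yes |

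The two operative phase definitions name BI 764524; the other three rules do not. The SAP does use wording that covers both arms where it means both, so BI 764524 cannot simply be read as shorthand for any study treatment.

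Counts on the literal reading:

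- Planned sham patients: 10 (SAP 6.1). With an on-treatment phase: 0.
- Post-baseline visits with vital signs and laboratory tests (Flow Chart II): Days 29, 57, 85, 113 and 155, which is 5.
- Planned sham patient-visits outside the on-treatment tables: 10 × 5 = 50 for vital signs and 50 for laboratory tests.
- Totals: SAP 6.1 lists three pairs, each with a total over all on-treatment phases and a total over those involving BI 764524 (overall, SRD, MD). As intended, only the SRD pair should coincide, because that part has no sham. Without a sham phase, "a total over all on-treatment phases in the MD part" equals its BI 764524 counterpart, and so does the overall total, so all three pairs coincide.

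**(b) Who is in the Treated Set?**

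- SRD patients treated: 12 (protocol 1.2; SAP 6.1 also gives 12 enrolled).
- SRD patients randomised: 0 (protocol 7.6).
- SRD patients meeting both conditions: 0 of 12. The denominator for dose-limiting events is then 0.
- Enrolled in total: 12 + 32 = 44 (SAP 6.1). The literal Treated Set can hold at most 32 of them.
- The pharmacokinetic set in protocol 7.3 is a subset of the Treated Set, so the same 12 are outside it.

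**Does this reach dose escalation?** No. Protocol 7.1 bases the Bayesian logistic model on patients evaluable for dose-limiting events, not on the Treated Set.

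**The case against.** The strongest reply is that the intent is plain and no one would program the literal reading. SAP 6.1 prints the arm-neutral rule above the phase list, says that phases are formed for each treatment, gives sham a label, and separates totals with BI 764524 from totals over everything. For the Treated Set, SAP 7.4.1 tabulates dose-limiting events per dose group and overall, which is meaningless if the SRD part is empty. This stands as evidence of intent. It does not repair the definitions: it shows that they disagree with the text around them, and no alternative Treated Set definition is given anywhere.

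A second reply is that laboratory and vital-sign data are assigned to visits by Table 6.7: 1, counted from first treatment, so every sham visit has a window. That is correct, and under that rule alone the 50 patient-visits are kept. But SAP 6.1 also limits those tables to the on-treatment phase, so the two rules conflict for sham patients.

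Third, no sham data would vanish from the report: the CTR Section 15.4 displays and the Appendix 16.2 listings include the screening period. This stands. What is at risk is the summary tables, among them the MD primary-endpoint table.

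Fourth, SAP 6.1 refers detailed treatment handling to the Technical TSAP ADS plan and the Analysis Data Reviewers guide, which may already be right. Neither document is available here, so whether anything is mis-programmed cannot be judged. Nor can much be made of the SAP showing no pharmacokinetic set definition of its own, since that text may have been redacted.

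**Conclusion.** Both definitions are wrong as worded and should be corrected. The sham phase affects the MD primary endpoint; the Treated Set affects the SRD primary endpoint.

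The sizes above are the literal consequence only. They rest on the planned 10 sham patients, because the SAP does not say how many of the 32 enrolled in the MD part received sham, and on full attendance at the five post-baseline visits. The practical effect is small if the programming follows the evident intent. The FAZ, visual acuity and retinal thickness models do not use the on-treatment phase, and the Treated Set wording does not exclude randomised, treated MD patients from them.

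**What to change.** - **SAP 6.1:** end Screening and start the on-treatment phase at the first trial treatment, whether BI 764524 or sham, and add an on-treatment phase carrying the existing *Sham MD* label.
- **SAP 6.3:** define the Treated Set as all SRD patients given BI 764524, plus all MD patients randomised and given one or more injections of BI 764524 or sham.
- **SAP Section 4:** record the Treated Set definition as a correction to protocol 7.3, where the same wording stands.
- **Technical TSAP ADS plan:** confirm that it uses the same start event and the same set.

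The cost is two wording corrections, one entry in Section 4 and one check of a technical document. No new data are needed and no clinical procedure changes.

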6.2 IMPORTANT PROTOCOL DEVIATIONS

Data discrepancies and deviations from the CTP will be identified for all treated patients.

Section 7.3 of the CTP:

Important protocol deviation (IPD) categories will be suggested in the Integrated Quality and Risk Management Plan (IQRMP), IPDs will be identified no later than in the Report Planning Meeting, and the IPD categories will be updated as needed.

Consistency check listings (for identification of deviations of time windows) and a list of protocol deviations (e.g. deviations in drug administration, in blood sampling times, etc.) will be provided to be discussed at the Report Planning Meeting and database lock meeting (RPM/DBLM). At latest at this meeting, all manual deviations identified at the sites by the CRAs and deviations too complex to program will be reviewed by the trial team to decide which are considered important. For definition of important protocol deviations (iPD), and for the process of identification of these, refer to the Boehringer Ingelheim (BI) SOP "Identify and Manage Important Protocol Deviations Deviations (iPD)" (3).

If any iPDs are identified, they are to be summarised into categories and will be captured in an accompanying Excel spreadsheet (DV sheet), where the categories which are considered to be iPDs in this trial are defined (4). The decision on the exclusion of subjects with iPDs from population sets will be documented in the decision log.

The iPDs will be summarised and listed.

